9.4. Treatment Compliance

Compliance will be evaluated overall for the Safety Set, ITT Set and Per Protocol Set.

Treatment compliance will be calculated as:

Compliance (%) = (# tablets taken / # tables to be taken according to the study schedule).

Where:

Life Sciences

tables taken = total number of tables taken between the date of first intake (included) and the date of last intake (included), as collected in the drug accountability CRF form.

tables to be taken according to the study schedule = date of Visit 10 - date of Visit 2 +1.

Date of Visit 10 will be replaced by the date of premature treatment discontinuation for patients who discontinued treatment prematurely.

In case a patient completed the treatment but missed Visit 10 or in case a patient prematurely discontinued treatment and presented an EOT date, as recorded in the related CRF form, which is considered as implausible (i.e.: EOT date greater than 25 days after the date of the first dose of the last kit), then the corresponding Visit 10 date or EOT date will be replaced with the date of last visit performed + 24 days.

If a subject returns all study medication that was dispensed, then the subject will not be classified as treated.

In case of missing drug accountability data, it will be assumed that no tablets were taken for the corresponding days with missing data.

For patients with kit(s) not returned, the information available in the drug administration CRF form about the documented tablet intake during the applicable study visit (i.e.: the study visit during which the first tablet from the kit – then never returned – was administered) will be used to add such one single day of documented treatment. For patients with kit(s) not returned and not having any information in the drug administration CRF form, i.e., there is no evidence that at least one tablet was taken, the number of tables taken will be assumed as 0.

A patient will be considered compliant with the therapy if his/her overall compliance is higher or equal to 80%.

Compliance will be reported numerically using descriptive statistics and categorically (using categories <80%, $\ge80\%$ to $\le100\%$, and >100%), by treatment group.

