11.1. Exposure

Duration of overall exposure (days) will be calculated as the difference between last tablet intake date and the first tablet intake date plus 1.

• Duration of overall exposure (days) = date of EOT - date first tablet intake +1

Duration of overall exposure will also be calculated in weeks using the following formula:

• Duration of overall exposure (weeks) = Duration of exposure (days) / 7

Duration of overall exposure, as defined above, will include any period of temporary treatment interruption.

The duration of overall exposure in days will be summarized using descriptive statistics by treatment groups.

A contingency table by treatment groups will also be presented with the following 3-weeks categories:

- [0-3)
- [3-6)
- [6-9
- [9-12)
- [12-15)
- [15-18)
- [18-21)
- [21-24)
- ≥24 weeks.

In addition, duration of actual exposure (in days and weeks respectively) will be also calculated similarly to the duration of overall exposure but removing any treatment interruption (i.e.: considering actual differences between dates of last and first tablet intake as reported in the drug accountability for each drug kit returned).

In case a patient prematurely discontinued treatment and presented an EOT date, as recorded in the related CRF form, which is considered as implausible (i.e.: EOT date greater than 25 days after the date of the first dose of the last kit), then for calculation of actual exposure the corresponding EOT date will be replaced with the date of last visit performed + 24 days.

For patients with kit(s) not returned but with information available in the drug administration CRF form about the documented tablet intake during the applicable study visit (i.e.: the study visit during which the first tablet from the kit – then never returned – was administered), this will be used to estimate the date of last intake from the kit, adding 24 days (as maximum number of tablets available in the kit to be

regularly taken) after the first intake. This approximation will be done to derive treatment interruptions for kit(s) that were not returned. This is applicable for actual exposure calculation only.

Exposure data will be listed for all subjects in the Safety Set.

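### SAP 11.1 dates the last intake from an unreturned kit one day too late and sets no limit at the next kit, end of treatment or death

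*SAP*

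**What the plan says.** SAP 11.1 defines two durations. Overall exposure is given by "Duration of overall exposure (days) = date of EOT - date first tablet intake +1". Actual exposure is "calculated similarly to the duration of overall exposure but removing any treatment interruption", and a bracket then explains this as "considering actual differences between dates of last and first tablet intake as reported in the drug accountability for each drug kit returned".

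For a kit that did not come back but whose first tablet was documented at a visit, the same section says "this will be used to estimate the date of last intake from the kit, adding 24 days". The reason given for 24 is "as maximum number of tablets available in the kit to be" taken regularly. The section adds: "This approximation will be done to derive treatment interruptions for kit(s) that were not returned", and restricts the rule to actual exposure. It names no upper limit for the estimated date. A separate rule replaces an EOT date that lies more than 25 days after the first dose of the last kit.

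SAP 9.4 treats the same kit differently for compliance: the documented intake "will be used to add such one single day of documented treatment". If no intake is documented, the kit counts as 0 tablets. A patient is compliant at 80% or more.

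**The concern.** The rule produces a calendar date, and that date can be impossible in three ways. It can lie after the tablets have run out, after the patient has opened the next kit, or after treatment or life has ended. If the date feeds a sum of kit durations, actual exposure can exceed overall exposure, although actual exposure is meant to be overall exposure with interruptions taken out. Two programmers could follow SAP 11.1 faithfully and obtain different tables.

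A lesser matter is that compliance credits the same kit with a single tablet. A reader who sets the exposure and compliance tables side by side will meet opposite assumptions with no explanation.

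**Working it through.** **Inputs**
- Kit content: tablets for one 3-week cycle (Protocol 5.4); at most 24 tablets (SAP 11.1).
- Visits: Days 1, 22, 43, 64, ..., 169, each with a +3-day window (Protocol flow chart).
- Unreturned kit: last intake = first intake + 24 days (SAP 11.1).
- Duration: last date − first date + 1. The + 1 is written for overall exposure and is carried over here to kits.
- Compliance: tablets taken / (Visit 10 − Visit 2 + 1) (SAP 9.4). For early stoppers the discontinuation date replaces Visit 10.
- Assumed for the examples: on-schedule visits, one tablet daily from Day 1, and EOT on the day of stopping (on or before the day of death).

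**1. The plan's 24.** 21-day cycle + 3-day window = 24 tablets. This matches the SAP, although the documents do not spell out the derivation.

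**2. The date.** Take a kit begun on Day 43.
- SAP rule: 43 + 24 = Day 67, and 67 − 43 + 1 = 25 days.
- 24 tablets: 43 + 23 = Day 66, and 66 − 43 + 1 = 24 days.

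**3. Overlap with the next kit.** Next kit on Day 64: 67 − 64 + 1 = 4 days. Next kit at the end of the window, Day 67: 1 day.

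**4. Actual exposure under the two possible calculations.**

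| Case | Overall | Kit durations summed | Overall to EOT minus gaps |
|---|---|---|---|
| Stops Day 60, Day 43 kit unreturned | 60 | 21 + 21 + 25 = 67 | 60 |
| Dies Day 50, Day 43 kit unreturned | at most 50 | 21 + 21 + 25 = 67 | at most 50 |
| Completer, two middle kits unreturned | 169 | 169 + 2 × (25 − 21) = 177 | 169 |

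**5. Does the implausible-EOT rule step in?** It needs more than 25 days from the first dose of the last kit to EOT. Here the intervals are 60 − 43 = 17 and at most 50 − 43 = 7, so it does not.

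**6. The extra day when gaps are subtracted.** If the next kit starts on Day 68, an estimated last intake on Day 67 shows no gap, although no tablet was left for Day 67. This needs a visit outside the window: the latest in-window visit is Day 67.

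**7. Compliance for the same kits.** Each unreturned middle kit loses 21 − 1 = 20 tablets.
- Completer, one lost kit: (169 − 20)/169 = 149/169 = 88.2%.
- Completer, two lost kits: (169 − 40)/169 = 129/169 = 76.3%, below 80%.
- Stop on Day 60: (21 + 21 + 1)/60 = 43/60 = 71.7%.
- Death on Day 50, with EOT that day: 43/50 = 86%.

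**8. With the date capped** (earliest of first intake + 23, day before next kit, EOT, death).
- Stop on Day 60: the kit runs Days 43–60 = 18 days; 21 + 21 + 18 = 60.
- Death on Day 50, with EOT that day: Days 43–50 = 8 days; 21 + 21 + 8 = 50.
- Completer: the Day 43 kit runs Days 43–63 = 21 days; total 169.

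In these cases the two calculations now agree.

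**The case against.** The best defence is that the estimated date was never meant to be added up. Its stated purpose is to find interruptions, and actual exposure is described as overall exposure, which ends at EOT, with interruptions removed. On that footing an overlap with the next kit simply means no gap, and nothing runs beyond EOT. Two details support this: replacing an implausible EOT date for actual exposure would serve no purpose in a pure sum of kit durations, and the kit-by-kit clause speaks of kits that were returned. This is a fair reading and may well be the intended one. It does not settle the matter, because the explanatory bracket describes kit-by-kit differences and the next rule supplies the missing end date for an unreturned kit.

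A reader might infer three stronger things that the documents do not support.
- **That exposure will run past death.** The estimated date can. Actual exposure does so only if kit durations are summed.
- **That safety results are distorted.** Adverse-event tables (SAP 11.2.3) use patient and event counts, no exposure-adjusted rate is planned, and the 3-week category table belongs to overall exposure.
- **That the exposure and compliance rules contradict each other.** The SAP openly confines the 24-day rule to actual exposure. Crediting only documented tablets is a conservative convention for adherence, and replacing it would be a trade-off: using documented days alone assumes that adherence in lost kits matched that in returned kits.

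It is also fair to say that the extra day is small and that the documents give no frequency of unreturned kits.

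**Conclusion.** The concern holds for the exposure rule. The estimated last intake is one day later than 24 tablets allow, overlaps an on-schedule next kit by 4 days (1 day if that visit is 3 days late), and can fall after EOT or death with no other rule to catch it. The effect on actual exposure is conditional. Summing by kit gives 67 against 60 days for the Day 60 stop and 67 against at most 50 for the Day 50 death; subtracting gaps within EOT gives no excess. The SAP does not say which applies.

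The reach is limited to the descriptive actual-exposure summary and its listing. No primary or secondary efficacy model uses exposure or compliance as a term. Whether compliance affects the Per-Protocol set cannot be told from the SAP, because the definitions of major deviations are in the blinded data review meeting minutes.

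On compliance, the 76.3% for a fully dosed completer with two lost kits is correct arithmetic. It calls for a label, not a new rule.

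**What to change.** **SAP 11.1.** State that actual exposure is overall exposure (ending at EOT) minus gaps between kits. Set the estimated last intake for an unreturned kit to the earliest of:
- first intake + 23 days;
- the day before first intake from the next kit;
- EOT;
- death.

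**SAP 9.4.** Keep the one-documented-tablet rule, but label it a worst-case assumption and say that it can class a fully dosed patient as non-compliant. Compliance over documented days only, with the undocumented days of unreturned kits left out of numerator and denominator, is an optional supplementary line.

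**Cost.** A few sentences of SAP text and a minor programming change. If the tables have already been produced, state in the study report which calculation was used and whether any patient's actual exposure exceeds overall exposure. The optional line adds one row to the compliance table, and its assumption about adherence in lost kits should be stated with it.

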11.2. Adverse Events

AEs will be coded using Medical Dictionary for Regulatory Activities (MedDRA) dictionary (version 22.0) to assign a preferred term (PT) and a system organ class (SOC) for each event.

11.2.1. Classification of Adverse Events

The reporting period for AEs is the period starting from the date/time of Informed Consent signature and lasting until Visit 11 (approximately 183 (+3) days post study drug administration on Day 1). All AEs (including SAEs) occurring within this period and not resolved by the end of the period will be documented on the eCRF as "ongoing".

Pre-Treatment AEs

An AE with onset date between date/time of Informed consent and the date of the first dose of the study drug (not included) is classified as a pre-treatment AE:

• Pre-treatment AE: AE onset date < date of the first dose of study drug;

Treatment-Emergent AEs

A treatment-emergent AE (TEAE) is an AE with onset date on or after the date of the first dose of the study drug and up to Study completion (last study visit being Visit 11: approximately Day 183 +3 days after first dose).

• TEAE: date of the first dose of study drug \leq AE onset date \leq date of completion

In case of treatment discontinuation an AE is classified as TEAE if:

• TEAE: date of the first dose of study drug ≤ AE onset date ≤ date of discontinuation +14 days

Notes:

- Events where the onset date is the same as the study drug start date are assumed to be TEAEs;
- By protocol 14 days is the post-treatment time-window for completers between Visit 10 (last dose) and Visit 11 (follow-up by phone call).

Any AE already present before the first dose of the study drug, that worsens in either intensity or frequency following exposure to the treatments is to be considered as new event classified as TEAE.

Post-Study AEs

HHELSINN

T AN001 Effective Date 25 JUL 2022 Approved Version 2.00

All AEs fulfilling the following conditions:

- onset date > study completion or
- onset date > treatment discontinuation+14 days

are classified as post-study AE.

In case of missing or incomplete dates not directly allowing allocation to any of the three categories of AEs, see the rules defined in Section 8.3.5.

Pre-treatment AEs, TEAEs and post-study AEs will be presented separately. Summary tables will be provided on TEAE only. Pre-treatment AEs and post-study AEs will be presented in the listings only.

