- ¹¹ Adverse events will be collected from Informed consent signature up to the end of the study Week 26 (Visit 11). SAEs must be reported within 24 hours.
- ¹² Baseline NSCLC treatment regimen will be captured at screening and adherence to this, and all future regimens will be captured throughout the treatment period.
- ¹³ Information on histological or cytological tumor type, genotype and treatment will be collected.
- ¹⁴ On study days that coincide with chemotherapy administration, all study procedures should be obtained prior to administration of chemotherapy. Patients should arrive for visits prior to dosing, and every effort should be made to have patient blood draws under fasted conditions; fasting status will be documented within the CRF. Patients who withdraw from study prematurely will be requested to complete the Day 64 visit (Week 9) procedures.

Study Design and Schedule of Assessments (Week 12 to 26)

Assessment	Visit Day ⁹ Treatment Period					Follow-up Period ¹⁰ (telephone)
Day	85 (+3)	106 (+3)	127 (+3)	148(+3)	169 (+3)	183 (+3)
Week	12	15	18	21	24	26
Visit	6	7	8	9	10	11
Physical exam ¹	Х	Х	Х	Х	Х	
Vital signs	Х	Х	Х	Х	Х	
Body weight ²	Х	Х	Х	Х	Х	
12-Lead ECG	Х	Х	Х	Х	Х	
Chemistry/Hematology ³	Х	Х	Х	Х	Х	
HbA1c	Х				Х	
Urine pregnancy testing (women of childbearing potential only)					Х	
Urinalysis ⁴					Х	
Administer FACIT questionnaires (includes all 4 domains, PWB, FWB, SWB, and EWB of FACT-G, 12-item A/CS domain and 13- item FACIT-F fatigue domain) and Hunger Assessment Scale questionnaires ⁵	Х	Х	Х	Х	Х	
CT scan ⁶	Х	\rightarrow	\rightarrow	\rightarrow	\rightarrow	
Adverse events ⁷	Х	Х	Х	Х	Х	Х
Concomitant medications (including chemotherapy) ⁸	Х	Х	Х	Х	Х	
Dispense new and/or return blister card for study drug dosing; check compliance	Х	Х	Х	Х	End	

¹ Physical Exam will focus on evaluation for any signs of pedal edema, pericardial effusion, pleural effusions, and ascites.

² Body weight will be measured in kg using a calibrated scale dedicated for use in this study and following study-specific procedures as described in APPENDIX 2.

- ³ All tests will be done under fasting condition. Hematology: CBC with differential count. Chemistry: sodium, potassium, chloride, calcium, total protein, albumin and pre-albumin, AST (SGOT), alkaline phosphatase (ALP), ALT (SGPT), total bilirubin, creatinine, C-reactive protein and glucose.

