9.4.6 Safety Analysis

The safety analysis will be performed on the Safety population.

Clinical evaluations for safety assessments will include adverse events (AEs) assessment, physical examination (PE), vital signs, 12-lead electrocardiogram (ECG), laboratory test (hematology, blood chemistry, urinalysis), Tumor assessments, Overall Survival.

Adverse events, 12-lead ECGs, vital signs, and laboratory assessments will be summarized by treatment group. All safety summaries and analyses will be performed based on the Safety Set. All safety and tolerability data will be listed. A treatment-emergent AE is one with an onset date on or after the date of the first dose of the study drug and up to Visit 11 (Day 183 +3 days) the last study visit.

AEs will be coded using Medical Dictionary for Regulatory Activities (MedDRA) dictionary (the version will be provided in the SAP and in the Data Management Plan [DMP]) to give a preferred term (PT) and a system organ class (SOC) for each event. The number and percentage of patients who experienced at least one TEAE, drug-related TEAE (defined as AEs with relationship classified by the investigator as definitely, probably, possibly, unassessable or missing), serious TEAE, serious related, severe TEAE (i.e. TEAE with CTCAE grade \geq 3), AESI (as described below), and the number and percentage of patients withdrawn due to TEAE will be summarized by treatment arm.

For each SOC and PT, summaries will be made with respect to the proportion of patients having at least one occurrence of that event during the study and the total number of events. The incidence of TEAEs in each treatment arm will be presented overall, by SOC and PT, and by additional grouping by severity according to the CTCAE grade and relationship to the study treatment. Tables of TEAEs will be presented by relationship to study drug. Additional tables including any relationship to study drug will be presented.

Adverse events of Special Interest are described in Section 8.1.2.1.

No formal test will be used for "between groups" comparison. All AEs will be listed.

Physical examination results at screening will be summarized in a frequency table (normal/abnormal). Results and relevant findings will be listed.

Vital signs will be summarized by treatment using descriptive statistics for absolute values and change from baseline (i.e., last value before first study drug intake).

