8.2.2. Intercurrent event study drug discontinuation

The treatment policy strategy will apply to address study drug discontinuation.

Due to the nature of the patients' underlying disease, a non-ignorable amount of missing data is expected in this trial. Every effort has been made to collect data from the protocol-specified assessments; patients were asked to continue to participate in the study and complete planned visits up to the end of the study period (Week 24) even if they have permanently discontinued treatment with the IMP ("retrieved dropout" approach).

Reason for treatment discontinuation will be collected in the CRF and will be considered for use in investigating possible unexpected patterns of missing data. To minimize the risk of bias in the analysis, specific rules for single/multiple imputation will be adopted

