11.2.3. Summaries of Adverse Events

A summary table reporting the total number of events, the total number of patients and the percentage of patients experiencing at least one of the following:

- Treatment-emergent adverse events (TEAEs)
- Drug-related TEAEs
- Serious TEAEs (SAEs)
- Drug-related SAEs
- TEAE CTCAE ≥ grade 3.
- TEAEs leading to treatment discontinuation
- Drug-related TEAEs leading to treatment discontinuation,
- Treatment-emergent AEs of special interest
- AEs with outcome Deaths

will be created by treatment group.

Drug-related TEAE are defined as AEs with relationship classified by the investigator as definitely, probably, possibly, unassessable or missing.

Each of the categories reported above will also be summarized in separate tables by SOC and PT:

By decreasing frequency for SOC;

By decreasing frequency for PT within the SOC;

Business & Decision

Life Sciences

Each summary table will be created by treatment group and overall.

For all adverse events, data will be prepared classifying events using MedDRA dictionary with respect to preferred term and SOC by treatment group.

Patients will be counted only once at the SOC level and will be counted once for each applicable preferred term; the total number of events will be presented for each SOC/PT.

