11.8. Overall Survival

Life Sciences

Business & Decision

Overall survival for the two treatment arms will be analyzed descriptively using Kaplan-Meier estimation. Efron method will be implemented for handling ties. Descriptive statistics will be provided as median time to event (and Interquartile Range). A summary of events and censored subjects will be given for each arm (n, %). K-M Plot with the survival curves for the two treatment arms will also be provided.

The difference in survival between anamorelin and placebo, descriptively assessed using a stratified Cox regression analysis (stratified by stratification factors listed in Section 8.4), will be provided as estimate of hazard ratio (HR) and 95%CIs.

Event or censor time in weeks will be calculated as follows:

- Event time (i.e. death) = ([date of death] [Study Treatment Start Date] +1 day)/7
- Event time (i.e. no death) = ([last follow-up contact date [Study Treatment Start Date] +1 day)/7

In this derivation, "Study Treatment Start date" instead of "Randomization date* is used because Overall Survival is considered as Safety variable.

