the level of treatment arms. Composite Clinical Response (CCR) definition was updated using final clinically meaningful thresholds for body weight gain (1.5 kg) and 5-IASS increase (3 points) resulted from the quantitative analysis of a separate study (7), combined with evidence from the embedded qualitative interview sub-study (6)

- With the aim to present a complete picture of the primary endpoint, the absolute change from baseline in body weight to Week 12 will also be presented for some pre-defined categories agreed during BDRM.
- Subgroup Analysis (Section 8.6): due to the inadequate number of patients within each subgroup, as described during the BDRM, the subgroups analysis (analysis of the coprimary and secondary efficacy endpoints in each stratum defined by the variable) will not be performed for the following variables:
 - o Race,

Business & Decision

Life Sciences

- o Ethnicity
- Country (Geographic region)
- Patients with at least one treatment emergent adverse event with preferred term related to fluid retention and/or patients with signs of edema.

Safety Analysis

- Laboratory Data: for Hematology and Blood Chemistry descriptive statistics based on absolute value and change from baseline by parameter and visits have been added. This analysis has been added because by protocol shift tables for only a subset of Hematology and Blood Chemistry parameters were planned.
- Overall Survival: an analysis, based on the stratified Cox regression model has been planned, in addition to the pre-planned analysis based on Kaplan-Meier estimates.
- Tumor assessments: The best overall tumor response summary as planned in the protocol has been replaced by the last overall response. This is because anamorelin is not expected to have an impact on tumor and the best response was finally not considered of safety interest.

HELSINN

T AN001 Effective Date 25 JUL 2022 Approved Version 2.00

14. **REFERENCES**

- 1. Ratitch B. Multiple Imputations. In: O'Kelly M and Ratitch B, editors. Clinical Trial with Missing Data: A Guide for Practitioners. West Sussex: John Wiley & Sons Ltd, 2014. p 185-256.
- Yang Yuan, SAS Institute Inc. Sensitivity Analysis in Multiple Imputation for Missing Data. SAS Proceedings, SAS Global Forum 2014: Paper SAS270-2014

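### For patients who stop study drug, the SAP closes the treatment-emergent window 14 days later instead of at Visit 11, which removes later adverse events from the by-arm tables without declaring the change

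*SAP*

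**What the plan says.** **Protocol.** Section 9.4.6 defines a treatment-emergent AE (TEAE) as one starting no earlier than the day "of the first dose of the study drug and up to Visit 11 (Day 183 +3 days) the last study visit". It gives no separate rule for patients who stop treatment. Collection runs over the same period (Study Flow Chart, footnote 11): "Adverse events will be collected from Informed consent signature up to the end of the study Week 26 (Visit 11". Section 6.3 asks investigators to keep contacting patients who stop drug, partly to pick up AEs.

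**SAP.** Section 11.2.1 gives the same collection period and first repeats the Visit 11 limit. It then sets a shorter one after treatment discontinuation: "TEAE: date of the first dose of study drug ≤ AE onset date ≤ date of discontinuation +14 days". Anything later is classed as *post-study*. A note explains that 14 days is the completers' interval from Visit 10 to Visit 11. AE summary tables are restricted to TEAEs, and "Pre-treatment AEs and post-study AEs will be presented in the listings only". On follow-up after stopping drug, Section 8.2.2 says "patients were asked to continue to participate in the study and complete planned visits up to the end of the study period (Week 24").

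Section 11.2.3 lists the rows of the overall AE table. One of them, "AEs with outcome Deaths", carries no treatment-emergent qualifier.

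The safety part of Section 13 declares changes to the laboratory, survival and tumour analyses, for example "The best overall tumor response summary as planned in the protocol has been replaced by the last overall response". The TEAE window is not among them.

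**The concern.** The two documents give different end dates for the main safety window, and the difference falls on patients who stop drug early and remain under observation. An AE starting on Day 80 in a patient who stopped on Day 43 is treatment-emergent under the protocol. Under the SAP it is post-study, even though SAP 8.8 defines study completion as completing Visit 11.

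AEs, serious AEs, events of Grade 3 or higher and AEs of special interest that start more than 14 days after stopping would be missing from the by-arm tables by system organ class and preferred term, by grade and by relationship. Fatal AEs may be missing too: the general restriction of tables to TEAEs suggests so, but the wording of that row leaves it open.

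Efficacy follows a treatment-policy strategy after discontinuation (SAP 5.1 and 8.2.2), so benefit and harm would be summarised over different periods for the same patients.

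**Working it through.** **1. Reproduce the 14 days.** Visit 10 is at Day 169 and Visit 11 at Day 183 (Protocol 6.1.10 and 6.1.11). 183 − 169 = 14, so the SAP's figure is correct as the completers' interval. For a completer at nominal visit days, both windows end on Day 183 and nothing is lost.

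**2. Days outside the tables for a discontinuer.** Let *d* be the day treatment stops and *L* the last contact day.

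- SAP window end = *d* + 14
- Days outside = max(0, *L* − (*d* + 14))
- Share of follow-up days outside = days outside / *L*

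The documents give no distribution of stop days or last-contact days, so both are illustrative.

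Stop at Day 43 (Week 6 visit), window end Day 57, varying last contact:

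| Last contact *L* | Days outside | Share of follow-up days |
|---|---|---|
| Day 57 | 0 | 0/57 = 0% |
| Day 85 | 28 | 28/85 = 33% |
| Day 127 | 70 | 70/127 = 55% |
| Day 183 | 126 | 126/183 = 69% |

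Followed to Day 183 (upper end), varying stop day:

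| Stop day *d* | SAP window end | Days outside | Share of 183 |
|---|---|---|---|
| 22 (Week 3) | 36 | 147 | 80% |
| 43 (Week 6) | 57 | 126 | 69% |
| 85 (Week 12) | 99 | 84 | 46% |
| 127 (Week 18) | 141 | 42 | 23% |
| 169 (Week 24) | 183 | 0 | 0% |

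If Visit 11 falls on Day 186, each count in the second table rises by 3 for a patient who has discontinued. These are calendar days, not shares of events or of patients.

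**3. Follow one late event through the SAP.** Onset after *d* + 14 makes it post-study (11.2.1). Post-study events go to listings only (11.2.1), so the event enters none of the by-arm AE tables that 11.2.1 confines to TEAEs. For the fatal-AE row in 11.2.3, the text does not settle which rule applies.

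**4. Check the declaration.** Protocol Section 9 says changes from planned analyses will be documented in the SAP and/or the study report. The rule is visible in SAP 11.2.1, but neither that section nor Section 13 identifies it as a departure from Protocol 9.4.6.

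**The case against.** - **The rule is open and reasoned.** SAP 11.2.1 states it with a rationale, and giving discontinuers the same 14 days after last dose as completers treats the two groups alike. The protocol does not require changes to be listed in one particular section. This stands as a defence of a +14-day set as an additional analysis. It does not justify replacing the protocol's definition without saying so.
- **Safety is descriptive.** Protocol 9.4.6 plans no formal between-group test of AEs, so no error rate depends on the window. This stands, but the by-arm tables remain the main safety comparison that readers will use.
- **Few events may be affected.** SAP 8.3.1 reports few retrieved dropouts, and SAP 8.8 allows the last contact to precede Visit 11 after discontinuation. If that contact falls within 14 days of stopping, nothing is lost. This stands as a limit on size, although the retrieved-dropout remark concerns efficacy assessments and does not count AEs gathered by telephone.
- **There is partial cover elsewhere.** Later AEs are listed, and deaths are counted by arm in the survival summary (SAP 11.8). The ALT/AST worst-grade tables and the glucose shift table (SAP 11.3) state no 14-day cut, so they bear on three of the nine AEs of special interest. This stands, but the glucose table shows only the last value, and the other six have no such cover.
- **The wider window takes in more disease-related events.** This is true, and it is a reason to show both windows.

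**Conclusion.** The concern holds. For patients who discontinue treatment, the SAP's TEAE window is shorter than the protocol's, later onsets leave the by-arm AE tables, and Section 13 does not declare the change. Following the SAP as written gives a safety comparison other than the one the protocol defines.

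The size in events is unknown and may be small. The day shares, 0% to 69% for a stop at Day 43, rest on assumed last-contact days and show only how far the windows can diverge. No discontinuation rate by arm is given, so a difference between arms cannot be assumed. Completers are not affected. Whether fatal AEs are cut is an ambiguity to resolve, not an established loss. This should be corrected before the tables are produced. Confidence is medium, because the number of late events cannot be judged from the documents.

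**What to change.** 1. Produce the by-arm tables for TEAEs, serious AEs, Grade 3 or higher, AEs of special interest and fatal AEs on the protocol window, first dose to Visit 11. Keep discontinuation + 14 days as a separately labelled on-treatment set. At minimum, keep the +14-day tables and add by-arm summaries of the later events.
2. State in SAP 11.2.3 which window governs the fatal-AE row.
3. Rename *post-study* to *post-treatment* for events that start before Visit 11.
4. Record the change from Protocol 9.4.6 in SAP Section 13, with the reason.

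The cost is one extra flag in the AE dataset, a repeat set of AE tables (or only the added summaries under the minimum option) and one line in Section 13. No new data are needed. The drawback is more output, with more disease-related events in the wider-window tables.
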